3.2 Sample Size

The objective of the study is to provide estimations with acceptable precision. Thus, the sample size is chosen to ensure that the width of the 95% confidence interval (CI) for the proportion of subjects who receive at least 1 RBC transfusion in each treatment group will be \leq 10% (ie, \pm 5% around the point estimate), assuming the proportion to be 25%. The choice of the precision of the estimated transfusion rate is based on clinical relevance and experience. The estimated proportion of 25% of subjects receiving at least 1 RBC transfusion is based on post hoc analyses in both treatment groups of Trial to Reduce Cardiovascular Events with Aranesp[®] Therapy (TREAT) of subjects who met the eligibility criteria for this study (Amgen data on file) and transfusion rates observed in other studies ([Provenzano et al, 2004](#), [Lawler et al, 2010](#)). To ensure the 95% CI with a width of \leq 10%, 300 subjects per group will be needed to enroll into the study. In order to ensure this precision can be maintained for sensitivity analyses, 20% drop out is accounted for, and enrollment of 375 subjects per treatment group is planned. This total sample size of 750 subjects will also ensure that the width of the 95% CI of the difference in transfusion incidence rates will be \leq 14% (ie, \pm 7% around the point estimate), assuming the proportion of subjects receiving at least 1 RBC transfusion during the study in both treatment groups is 25%. All confidence intervals are derived using normal approximation.

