5. HYPOTHESES AND/OR ESTIMATION

The incidence of RBC transfusions in each treatment group (Hb-based titration group and fixed dose group) and their difference will be estimated, and no formal hypothesis will be tested. The width of the 95% CI of the transfusion incidence rate is expected to be < 10% (ie, $\pm 5\%$ around the point estimate) in each group and the width of the 95% CI of the difference in transfusion incidence rates is expected to be < 14% (ie, $\pm 7\%$ around the point estimate). The efficacy and safety of each treatment group will be described, as these aspects will assist in the determination of a preferred dosing regimen.

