For time to event such as time to first transfusion, or time to first major clinical event (eg, major adverse cardiovascular events (MACE), all-cause mortality), time to event is derived from the randomization date to the date of specific event. Subjects that do not experience the event will be censored. For time to event analysis using the on-treatment approach, the censoring date is the last dose date + 3 months (84 days) or the end of study date, whichever is earlier. For time to event analysis using the on-study approach, the censoring date is the end of study date.

Context surrounding RBC Transfusion

Clinical context surrounding RBC transfusion will be collected for each RBC transfusion event, and will be reviewed by an independent Clinical Endpoint Committee (CEC). The clinical context includes the primary reason for the transfusion event, the transfusion setting (eg, dialysis center, intensive care unit, emergency department), Hb at the time of the first transfusion of the transfusion event, clinical events (eg, bleeding, surgery), symptoms and vital signs of concerns.

Total number of units of RBC transfused

The total number of units of RBC transfused using the on-treatment approach is the sum of RBC units transfused between the randomization date and the earlier date of the last dose date + 3 months (84 days) and the end of study date. The total number of units of RBC transfused using the on-study approach is the sum of RBC units transfused between the randomization date and the end of study date.

Number of Days Hospitalized

This is the total number of days of hospitalization between the randomization date and earlier of the date of last IP + 3 months (84 days) and the end of study date for the on-treatment approach; between the randomization date and the end of study date for the on-study approach. Duration of each hospitalization stay is calculated as day of discharge - day of admission + 1. Hospitalizations with identical admission and discharge days will be counted as a hospitalization with duration of 1 day.

Area under the Curve (AUC) Calculation

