10. STATISTICAL METHODS OF ANALYSIS

10.1 General Principles

Descriptive statistics will be presented for all endpoints by treatment group. For continuous variables, these include number of observations, mean, standard error (SE) and/or standard deviation (SD), median, 25th percentile (Q1), 75th percentile (Q3), minimum and maximum. For categorical variables, the frequency and percentage are presented. For time to event endpoints: Kaplan-Meier curves, Kaplan-Meier percentiles, the number of subjects censored, and the number of subjects with events will be summarized. Confidence intervals will be constructed as 2-sided at the 95% level. Summaries of laboratory data, Hb and dose related parameters, and vital signs will be completed using the full analysis set, limited to measurements obtained while the subject is receiving the investigational product.

For variables that are summarized over time, the actual visit for a subject may not exactly coincide with their targeted scheduling. The visit windows defined in [Appendix A](#) will be used to assign evaluations to a most appropriate nominal visit for analysis and summarization.

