10.5.2 Analyses of Secondary Efficacy Endpoint(s)

Total number of units of RBC transfused per subject will be described for each treatment group, and will be analyzed using a negative binomial regression model which will

include the stratification factors used at randomization. As a sensitivity analysis, exposure adjusted event incidence of total number of units RBC transfused will be presented with 95% CI using Chi-square approximation to the Poisson distribution. These analyses will be performed using both on-treatment approach with the full analysis set and on-study approach with all randomized subjects.

Time to first RBC transfusion will be analyzed using both on-treatment approach with the full analysis set and on-study approach with all randomized subjects. It will be analyzed by each treatment group with Kaplan-Meier curves, Kaplan-Meier percentiles and estimates at 6, 12, 18, and 24 months, the number of subjects censored, and the number of subjects transfused. A supportive analysis will be performed using Cox proportional hazards model (Cox, 1972) stratified by the stratification factors used at randomization to evaluate the difference between the treatment groups. The hazard ratio and its corresponding 95% CI will be estimated.

Average achieved Hb concentration while receiving investigational product will be described as average Hb using the area under the curve (AUC) method. The median of the difference in achieved Hb concentration (Hodges–Lehmann estimate) between treatment groups will be calculated and 2-sided 95% confidence limits will be derived by using a nonparametric Wilcoxon rank-sum statistic (Hollander and Wolfe, 1973). As a sensitivity analysis, the above analyses will be repeated excluding Hb concentrations measured within 3 months (84 days) from an RBC transfusion.

Cumulative doses of darbepoetin alfa adjusted for investigation product exposure time (eg, average cumulative darbepoetin alfa dose per 4 week) will also be summarized, and the median of the difference (Hodges–Lehmann estimate) between treatment groups will be calculated and 2-sided 95% confidence limits will be derived by using a nonparametric Wilcoxon rank-sum statistic.

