10.6.2 Major Clinical Events

Time to adjudicated major clinical events (as specified in [Section 4.3](#)), will be summarized by each treatment group with Kaplan-Meier curves, Kaplan-Meier percentiles, the number of subjects censored, and the number of subjects with events, using both on-treatment approach with the full analysis set, and on-study approach with

all randomized subjects. Subgroup analyses for the initial Hb response subgroup will be presented using both on-treatment and on-study approaches and the initial Hb response analysis set.

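### Event-free deaths are in effect censored, so the Kaplan-Meier estimates for first transfusion and the component clinical events overstate actual cumulative incidence; add competing-risk estimates.

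*SAP*

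**What the plan says.** SAP 6.3 (Time to Event Derivation) measures time from randomization and states: "Subjects that do not experience the event will be censored". The on-study censoring date is the end of study date. The on-treatment date is the earlier of last dose plus 84 days and the end of study date. Death has no rule of its own. SAP 6.1 takes the end of study date from the End of Study eCRF, and protocol 8.1 lists death among the reasons for removal from the study.

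Three parts of the SAP use this rule:

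- **SAP 10.5.2:** "Time to first RBC transfusion will be analyzed using both on-treatment approach with the full analysis set and on-study approach with all randomized subjects". The output is Kaplan-Meier curves, percentiles and estimates at 6, 12, 18 and 24 months, plus a stratified Cox model.
- **SAP 10.5.1:** the same methods are applied, on-treatment only, to first transfusion or stopping investigational product for lack of efficacy.
- **SAP 10.6.2:** the paragraph that begins "Time to adjudicated major clinical events (as specified in" gives Kaplan-Meier curves, percentiles and counts, without a hazard ratio.

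The visible text contains no competing-risk method. The code in Appendix B is redacted, so nothing can be concluded from it.

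**The concern.** A subject who has died can no longer be transfused or have a stroke. Kaplan-Meier treats that subject like one lost from view who could still have the event. One minus Kaplan-Meier (1-KM) therefore estimates risk with death removed, and it exceeds the share of subjects who actually have the event whenever some die first.

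This matters because the stated objective is the incidence of transfusion. Protocol 2.3 also says the preferred regimen will be judged on transfusion and adverse outcomes together. Readers are likely to take a Kaplan-Meier value at 12 or 24 months as an incidence, and to take the gap between two curves as a difference in incidence.

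**Working it through.** **The plan's own figures, for scale.** The study is one of estimation: "no formal hypothesis will be tested", and "Confidence intervals will be constructed as 2-sided at the 95% level". The SAP states that "300 subjects per group will be needed to enroll into the study" and that "20% drop out is accounted for, and enrollment of 375 subjects per treatment group is planned". At the assumed 25%:

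- Per-group CI width at n = 300: 2 × 1.96 × √(0.25 × 0.75 / 300) = 9.80 points (target 10).
- Dropout: 300 / 0.80 = 375.
- CI width for the difference, 2 × 1.96 × √(2 × 0.25 × 0.75 / n): 13.86 points at 300 per group and 12.40 at 375 (target 14).

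The plan's figures reproduce. They concern the crude proportion, not Kaplan-Meier.

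**Inputs for the check.** Transfusion incidence is 25% (SAP 3.2) and on-study follow-up is 100 weeks (protocol 3.4.1). Mortality is not given, so 5% to 30% over 100 weeks is assumed. Deaths are taken as censored at the death date, and hazards as constant. The calculation fits the on-study approach only.

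**Formulas.** Let L and M be the cumulative hazards of transfusion and death over 100 weeks, with M = -ln(1 - D) for death risk D.

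- 1-KM = 1 - exp(-L)
- Actual cumulative incidence = L/(L+M) × [1 - exp(-(L+M))]

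Example with D = 15%: M = 0.1625. Actual incidence is 25.0% when L = 0.3143, since 0.3143/0.4768 × (1 - exp(-0.4768)) = 0.659 × 0.379 = 0.250. Then 1-KM = 1 - exp(-0.3143) = 27.0%.

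| Assumed death risk | M | L | 1-KM when actual is 25.0% | Excess (points) | 1-KM when actual is 5.0% |
|---|---|---|---|---|---|
| 5% | 0.0513 | 0.2959 | 25.6% | 0.6 | 5.1% |
| 10% | 0.1054 | 0.3048 | 26.3% | 1.3 | 5.3% |
| 15% | 0.1625 | 0.3143 | 27.0% | 2.0 | 5.4% |
| 20% | 0.2231 | 0.3247 | 27.7% | 2.7 | 5.6% |
| 30% | 0.3567 | 0.3484 | 29.4% | 4.4 | 5.9% |

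The last column illustrates a rarer event such as stroke; the 5% is also an assumption.

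**Between groups, assumed mortality 10% versus 20%.**

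1. *Independent risks, equal transfusion hazards.* 1-KM is 25.0% in both groups. Actual incidence is 23.8% versus 22.5%, 1.3 points apart. Kaplan-Meier is not moved by mortality; actual incidence is.
2. *Independent risks, equal actual incidence of 25%.* 1-KM is 26.27% versus 27.73%, 1.46 points apart. The cause-specific hazard ratio is 0.3247/0.3048 = 1.07.
3. *Correlated risks* (shared gamma frailty, variance 0.5 to 1.0, simulated with 2,000,000 subjects; equal underlying transfusion risk of 25%). 1-KM runs from 24.5% versus 24.0% to 24.1% versus 23.1%, a spurious gap of 0.5 to 1.0 points. Actual incidence is 23.4% versus 21.7%, and 23.1% versus 21.1%. 1-KM is above actual incidence in each case.

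**The case against.** **The incidence objective is already served.** The primary analysis (SAP 10.5.1) is a crude proportion. Subjects who die untransfused stay in its denominator, so Kaplan-Meier cannot inflate it. All-cause mortality and both composites containing death are also unaffected, and the SAP nowhere calls 1-KM an incidence. This stands. It limits the point to the secondary endpoint, the lack-of-efficacy analysis and the component clinical events. It also means that setting the excess against the plan's ±5-point precision target would mix two different estimators.

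**A reader might infer that unequal mortality by itself distorts the comparison between strategies.** The documents do not support this. With independent risks, unequal mortality leaves the Kaplan-Meier curves where they are (case 1), and the Cox model gives a valid cause-specific hazard ratio. The comparison misleads only if gaps between curves are read as incidence differences, or if the risks of death and of the event are correlated. Correlation is plausible here, but the documents do not establish it.

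**Between-group effects are probably small.** The two earlier outcome trials described in protocol 2.3 report hazard ratios of 1.34 and 1.05 for outcomes that include death. Suppose 1.34 applied to death alone (an assumption), with base death rates of 5%, 10% or 15% per year, equal transfusion hazards and 1-KM of 25% at Day 701. Actual incidence would then differ by 0.4, 0.7 or 0.9 points. The planned half-width for the difference is 12.40 / 2 = 6.2 points. This stands too.

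**The alternative has its own cost.** Cumulative incidence falls as mortality rises, so in case 1 it makes the group with more deaths look 1.3 points better on transfusion. That is a reason to report it with mortality, not a reason to leave it out.

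**Censoring at death is an inference.** The end of study date is an eCRF entry that the SAP does not tie to the death date. If it were recorded later than death, the subject would stay in the risk set and the excess would shrink. The rule therefore needs to be written down.

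**Conclusion.** The point holds in a limited form. Event-free deaths are in effect censored and no competing-risk estimator is visible. 1-KM therefore overstates actual cumulative incidence for first transfusion, transfusion or lack-of-efficacy discontinuation, stroke, myocardial infarction, decompensated heart failure, thromboembolic events, vascular access thrombosis and cardiovascular mortality (where non-cardiovascular death competes).

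The direction is known. At a true 25% the size is 0.6 to 4.4 points, and about 2 points at 15% mortality. A 10-point mortality gap would change the comparison by about 0.5 to 1.5 points. All of these figures rest on assumed mortality and on censoring at the death date; the range at 25% also assumes constant, independent hazards.

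The documents support neither a claim that the primary result is biased nor a claim that mortality differences alone distort the curves.

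**What to change.** - **SAP 6.3:** state that event-free deaths within the evaluation period are handled as competing events at the death date.
- **SAP 10.5.1 (transfusion or lack-of-efficacy analysis), 10.5.2 and 10.6.2:** add Aalen-Johansen cumulative incidence by group, with death as the competing event (non-cardiovascular death for cardiovascular mortality). For transfusion, include the 6-, 12-, 18- and 24-month estimates.
- **Cox models:** label the hazard ratios as cause-specific.
- **Presentation:** show these results beside all-cause mortality by group.
- **Kaplan-Meier:** keep it for all-cause mortality and the composites that contain it. Elsewhere it may remain as supplementary output.

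This is a cheap improvement. Protocol 7.2.11 already has deaths collected for adjudication, so no new data are needed and the sample size is unchanged. The cost is a little more analysis and more care in interpretation, because higher mortality lowers cumulative incidence. The change does not deal with on-treatment censoring 84 days after the last dose for reasons other than death.

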7. ANALYSIS SUBSETS

7.1 Full Analysis Set

The full analysis set will include all randomized subjects who receive at least 1 dose of investigational product. Subjects will be grouped according to their randomized treatment assignment. The full analysis set will be used in the primary analysis and safety analysis.

7.2 Completer Analysis Set

The completer analysis set will include all randomized subjects who receive at least 1 dose of investigational product and either complete the investigational product administration, or end investigational product due to death. Subjects will be analyzed according to their randomized treatment assignment.

7.3 Initial Hb Response Analysis Set

The initial Hb response analysis set will include all randomized subjects who receive at least 1 dose of investigational product, excluding those who ended investigational product prior to Week 5 or those who do not have Hb measurement at Week 5.

Subjects will be analyzed according to their randomized treatment assignment. Subjects

will be excluded if: they do not receive the first dose at Day 1, they receive RBC transfusion during the period from randomization to prior to Week 5, they end investigational product prior to Week 5, or they do not have a Hb measurement at Week 5.

8. INTERIM ANALYSIS AND EARLY STOPPING GUIDELINES

Prior to the completion of the recruitment period, the sponsor may conduct a reassessment of the study assumptions (eg, transfusion rate) based on blinded aggregated data and revise the sample size in order to ensure that the desired precision of transfusion rate estimates can be achieved.

An external independent Data Monitoring Committee (DMC) will be established to review the unblinded study data throughout the duration of the study and the DMC may request additional data. If warranted, the DMC can recommend modifying or stopping the study, or suspending enrollment. This recommendation may be based on any safety concerns, lack of efficacy/futility, or preponderance of early evidence of efficacy. The DMC will convene approximately once every 3 to 6 months. The DMC will oversee an interim analysis to assess whether the study objective is likely to be achieved based on the totality of the data. This interim analysis will occur when approximately 33% of subjects have completed 12 months of planned study follow-up

Analyses for the DMC will be provided by an external Independent Biostatistics Group (IBG). The IBG and DMC will have access to subjects' individual treatment assignments. To minimize the potential introduction of bias to the conduct of the study, members of the DMC and IBG will not have any direct contact with study center personnel or subjects. The DMC will communicate major safety concerns and recommendations regarding study modification or termination based on the safety and efficacy parameters to Amgen in accordance with the DMC charter.

Records of all meetings will be maintained by the DMC for the duration of the study. Records of all meetings will be stored in the Amgen official document management system at the conclusion of the study. Further details are provided in the DMC charter.

9. DATA SCREENING AND ACCEPTANCE

9.1 General Principles

The objective of the data screening is to assess the quantity, quality and statistical characteristics of the data relative to the requirements of the planned analyses.

9.2 Data Handling and Electronic Transfer of Data

Amgen's Clinical Data Management (CDM) department will provide all data to be used in the planned analyses. This study will use the RAVE database.

All data collected in the eCRF will be extracted from RAVE. Important protocol deviations will be transferred from eClinical. Unblinded subject and box ID randomization lists will be provided by Amgen's randomization group upon unblinding of the study. See Data Transfer Plan (DTP) and Data Management Plan (DMP) for details.

9.3 Handling of Missing and Incomplete Data

9.3.1 Patterns of Missing Data

Subjects may be missing specific data points for various reasons. In general, data may be missing due to a subject's early withdrawal from study, a missed visit, or nonevaluability of a data point at a particular point in time. In the Data Quality Review (DQR) process, queries will be made to the sites to distinguish true missing values from other unknown values (eg, due to measurement or sample processing error). All attempts will be made to capture missing or partial data for this trial prior to the database lock.

The frequency and pattern of missing data such as reasons for investigational product not given, and missing response to the question regarding at each study visit while receiving investigational product will be assessed through descriptive summaries over time.

9.3.2 Handling of Missing Data

For all time-to-event outcomes, there will be no imputation of data, except incomplete dates. Missing values will not be imputed and no imputation will be done for the AUC calculation. Missing safety endpoints will not be imputed.

9.3.3 Handling of Incomplete Dates

Adverse events with a valid answer to the question "Did event start before first dose of investigational product?" on eCRF can be well defined based on the answer regardless of dates being completely or partially missing. Adverse events for which the start date is entirely missing will be counted as occurring on the date of first investigational product

administered. Adverse events with a partially missing start date that is conclusively prior to the date of first investigational product administered will be considered pre-treatment adverse events and excluded from safety analyses. All other partially missing adverse event dates will be handled as described below, with the reference date being the date of first investigational product administered:

- If the adverse event year is available and the day and month are missing, the day and month will be set to the 1st of January of the onset year.
- If the year and month are available and the day is missing, the day will be set to the 1st of the onset month.
- If the day and month are available and the year is missing, the year will be set to the year of the reference date.
- If the year and day are available and the month is missing, the month will be set to January of the onset year
- If the resulting date is prior to the reference date, the date will be reset to the reference date.
- If the imputed adverse event end date is prior to the imputed adverse event start date, the imputed end date will be reset to the imputed start date.

Concomitant medication with completely or partially missing dates will be queried. If after the query is resolved, the date is still incomplete with year only or year and month only, the concomitant medication start date will be imputed using the algorithm above, with the reference date being the randomization date.

All missing and partially missing onset dates of time-to-event outcomes will be queried. If after the query is resolved, the event onset date is still incomplete, this date will be imputed using the algorithm above with the reference date being the randomization date. Partial/missing death date and missing fatal AE end date will be imputed to be the last known date on study, or the imputed date as defined above, whichever is later.

Medical history partial/missing dates will be imputed using the algorithm above, with the reference date being one day prior to the randomization date.

Hospitalization and transfusion partial/missing dates will be imputed using the above algorithm as well with the reference date being randomization date.

No other date imputation will be done.

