eGFR	estimated Glomerular Filtration Rate
Electronic Source Data (eSource)	Source data captured initially into a permanent electronic record used for the reconstruction and evaluation of a trial.
Electronic Trial Operations (ETO) System	An electronic system that is used to facilitate the operations of a clinical trial through the collection of study related data. Most common applications of an ETO system within a clinical trial are: subject randomization and product management. Term synonymous with the industry term IVR or IVRS. Note: An individual can interface with an ETO system by using either an IVR or IWR interface. See definitions of IVR and IWR below.
End of Study for individual subject (EOS)	Defined as the last day that protocol specified procedures are conducted for an individual subject
End of Study (primary completion)	Defined as the date when the last subject is assessed or receives an intervention for the purposes of final collection of data for the primary endpoint
Enrollment	Defined as the date the subject is randomly assigned to a treatment group or "randomized"
EPO	Erythropoietin
ESA	Erythropoiesis Stimulating Agent
ET	Early Termination
GCP	Good Clinical Practice
GI	Gastrointestinal
Hb	Hemoglobin
HBV	Hepatitis B Virus

Abbreviation or Term	Definition/Explanation
HCT	Hematocrit
HCV	Hepatitis C Virus
HemoCue	Modified hemoglobin point of care device
HIV	Human Immunodeficiency Virus
HLA	Human Leukocyte Antigen
HTLV	Human T-Lymphotropic Virus
ICF	Informed Consent Form
ICH	International Conference on Harmonisation
IEC	Independent Ethics Committee
Interactive Voice Response (IVR)	Telecommunication technology that is linked to a central computer in real time as an interface to collect and process information.
Interactive Web Response (IWR)	Web based technology that is linked to a central computer in real time as an interface to collect and process information.
IP	Investigational Product
IRB	Institutional Review Board
IV	Intravenous
KDOQI	The National Kidney Foundation Kidney Disease Outcomes Quality Initiative
MACE	Major Adverse Cardiovascular Events
MCH	Mean Corpuscular Hemoglobin
MCHC	Mean Corpuscular Hemoglobin Concentration
MCV	Mean Corpuscular Volume
MedDRA	Medical Dictionary for Regulatory Activities
MI	Myocardial Infarction
MPV	Mean Platelet Volume
ND-CKD	Chronic Kidney Disease Not on Dialysis
PFS	Prefilled Syringe
PIN	Personal Identification Number
POC	Point of Care
PSD	Protocol Specified Dose

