6. DEFINITIONS

6.1 Study Time Points

Informed Consent Date

The informed consent date for each subject is the date the subject signs the original informed consent for this study.

Enrolled

Individuals are considered enrolled if they have been assigned a randomization number and have a non-missing randomization date. Enrolled individuals are referred to as "subjects".

Randomization (Enrollment) Date

The randomization date for each subject is the date the investigator (or designee) confirms in the IVRS that the subject has met all eligibility criteria and is randomized.

Study Day 1

Per protocol, all subjects must receive the first dose of investigational product on the date of randomization. Therefore, for each subject, Study Day 1 will be defined as the day of randomization.

Study Day

For each subject and for a given study visit date, study day is defined as the number of days since Study Day 1:

$$\text{Study day} = (\text{study visit date} - \text{Study Day 1 date}) + 1$$

If the date of interest is prior to the Study Day 1:

$$\text{Study day} = (\text{study visit date} - \text{Study Day 1 date}).$$

Date of Last Dose of Investigational Product Received

For each subject, the date of last dose of investigational product received is defined as the date of last administration of the investigational product during the study.

End of Investigational Product (EOIP) Date

For each subject, the end of investigational product date is defined as the date recorded on the End of Investigational Product Electronic Case Report Form (eCRF).

End of Study (EOS) Date

For each subject, the end of study date is the date recorded on the End of Study eCRF.

Study End Date

The study end date is the last end of study date of all randomized subjects.

Study Month

One study month is defined as 4 weeks (28 days)

Last Known Date

Defined as the last available complete date in the clinical database for a subject, eg, date a scheduled measurement is taken or an investigational product is administered, concomitant date, adverse event date, end of study date, reported endpoint onset date, etc.

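### The SAP's rule for partial death dates has no cap at the known month or year, so a later database date can move a death past its known month and, less often, out of the on-treatment window

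*SAP*

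**What the plan says.** Four statements in the SAP act together.

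- **Imputation algorithm (SAP 9.3.3).** "If the year and month are available and the day is missing, the day will be set to the 1st of the onset month". With only the year known, the date becomes 1 January of that year.
- **Death rule (SAP 9.3.3).** A partial or missing death date "will be imputed to be the last known date on study, or the imputed date as defined above, whichever is later".
- **Last known date (SAP 6.1).** "Defined as the last available complete date in the clinical database for a subject". The examples include "concomitant date, adverse event date, end of study date, reported endpoint onset date". The end-of-study date is in turn taken from a form: "For each subject, the end of study date is the date recorded on the End of Study eCRF".
- **On-treatment censoring (SAP 6.3, Time to Event Derivation).** "the censoring date is the last dose date + 3 months (84 days) or the end of study date, whichever is earlier".

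SAP 10.6.2 applies both the on-treatment and the on-study approach to the major clinical events of SAP 4.3. These include all-cause mortality, cardiovascular mortality and two composites that contain death.

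**The concern.** Taking the later of two dates is sound when the second is a date on which the subject was known to be alive, because it prevents a death from being dated before a documented contact. The last known date in SAP 6.1 is not limited in that way, and the rule has no upper bound. It can therefore replace a known month of death with a later date.

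A late database date is plausible in this trial. Protocol 8.1 has subjects who stop investigational product followed at least for transfusions and adjudicated endpoints. It allows this through family or friends, other physicians or review of records. A site can then learn of a death some time afterwards, know only its month, and complete an end-of-study form with a later date.

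At stake are the on-treatment summaries of all-cause mortality, of cardiovascular mortality where the death was cardiovascular, and of both composites where no earlier component event had occurred. These are described by arm without a formal test, so a single displaced death changes the displayed count.

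**Working it through.** **The plan's own figure.** SAP 6.1 sets a study month at 28 days. 3 × 28 = 84 days, which agrees with SAP 6.3.

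**The rule as a formula.** With only the day missing:

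- imputed death date = max(1st of known month, last known date)
- the death leaves its known month if the last known date is after the last day of that month
- the death leaves the on-treatment window if the imputed date is after last dose + 84 days

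**Illustration (dates invented).** Last dose 20 Nov 2013; death recorded as Jan 2014; end-of-study form dated 20 Mar 2014, the latest date in the database.

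- Window end: 20 Nov 2013 + 84 days = 12 Feb 2014 (10 days to 30 Nov, 31 to 31 Dec, 31 to 31 Jan, 12 to 12 Feb; 10 + 31 + 31 + 12 = 84).
- Every day of January 2014 lies inside the window, so the death is certain to be on-treatment.
- Imputed date: max(1 Jan 2014, 20 Mar 2014) = 20 Mar 2014. This is 48 days after 31 Jan and 78 days after 1 Jan, so the death is dated about 7 to 11 weeks late.
- 20 Mar is after 12 Feb, so the subject is censored event-free in the on-treatment analysis.

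**Cases where less or nothing goes wrong.**

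- Last dose 6 Jan 2014 (window ends 31 Mar), death in March, form dated 28 Mar: the imputed date is 28 Mar, inside both the month and the window.
- Last dose 3 Mar 2014 (window ends 26 May), death in March, form dated 15 Apr: the imputed date leaves March but stays in the window.
- Last database date 15 Dec, true death 20 Jan recorded as January: the imputed date is 1 Jan, 19 days early.

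**How often, if a late form date exists.** The documents give no delay from death to the recorded end-of-study date, so 0 to 90 days is an assumed range. Further assumptions: only the day of death is missing, the form date is the latest database date, deaths are spread evenly over a 365-day year, and the gap from last dose to death is spread evenly over 0–28 or 0–84 days. All these deaths truly fall inside the window.

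- Past the known month: for a delay of 7 days, 12 × 7 / 365 = 23%; for 14 days, 12 × 14 / 365 = 46%; for 30 days, 358 / 365 = 98% (only the first day of each of the seven 31-day months escapes).
- Out of the window: requires gap + delay > 84. With gaps of 0–84 days and a delay of 30 days, 30 of 85 gaps qualify = 35%. With gaps of 0–28 days and a delay of 60 days, 4 of 29 qualify = 14%.

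| Delay (days) | Past known month | Out of window, gap 0–84 | Out of window, gap 0–28 |
|---|---|---|---|
| 0 | 0% | 0% | 0% |
| 7 | 23% | 8% | 0% |
| 14 | 46% | 17% | 0% |
| 30 | 98% | 35% | 0% |
| 60 | 100% | 71% | 14% |
| 90 | 100% | 100% | 100% |

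These are percentages of deaths that already have an incomplete date and a late form, not of all deaths. Dosing is every 4 weeks, so the last column is the closer guide for deaths during ongoing dosing, and the 0–84 column for deaths after product is stopped.

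**The case against.** The strongest reply is that a late end-of-study date is not what the protocol intends. Its glossary gives the subject's end of study as "Defined as the last day that protocol specified procedures are conducted for an individual subject". Read strictly, that is normally a contact before death, and the later-of rule then does its proper job. Nor does the shift arise if sites enter the death date itself. SAP 9.3.3 also speaks of the last known date on study, and Protocol 8.1 lists death as a reason for removal from the study, so the qualifier could be read as excluding dates after death. This stands as a reason to expect few cases. It does not close the gap: SAP 6.1 ties the end-of-study date to whatever is on the form, names it as a last known date, and does not require it to precede or equal death.

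The safeguards also stand. Incomplete event dates are queried first (SAP 9.3.1 and 9.3.3), deaths are adjudicated (Protocol 7.2.11), the major-event analyses are repeated on-study in all randomized subjects (SAP 10.6.2), and fatal adverse events are tabulated separately (SAP 10.6.1).

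A reader might infer that the rule always delays deaths or removes them from the on-treatment count. It does not: when the last known date precedes the known month, the rule returns the 1st of that month, which can be early and could even bring a death into the window. A reader might also want to say how many deaths would be lost. The documents give neither an expected number of deaths nor a proportion with incomplete dates, so no such count can be supported. Nor is every date listed in SAP 6.1 unsuitable: the onset of a non-fatal endpoint is good evidence that the subject was alive.

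**Conclusion.** The rule is wrong as written for one situation: a death with a known month or year and a database date after it. The imputed date then contradicts what is known. If the database date is also later than last dose + 84 days, a death certain to be on-treatment is lost from the on-treatment summaries that include it. The on-study analyses generally retain the death, with a late event time.

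The point is minor. It rests on some end-of-study or other database dates falling after death, which the documents permit but do not show to be usual. It is confined to descriptive safety endpoints; the primary transfusion endpoint does not use the death date.

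**What to change.** In SAP 9.3.3, replace the rule for partial death dates with:

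*A partial death date is set to the later of the algorithm date and the last date the subject was documented alive (visit, dose, sample, contact or onset of a non-fatal event), but not later than the last day of the known month (or year). An end-of-study date is used only if it reflects a contact with the living subject.*

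In the illustration, the imputed date then cannot be later than 31 Jan 2014, and the death counts as on-treatment. If a documented-alive date falls after the known month, the two records conflict and should be queried.

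The cost is two sentences in the SAP and a few lines of code, with no new data collection. It is best done before unblinding.
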